16.4. Surgical Assessment Questionnaire

Question	Response
	High
Expected probability of a complete resection	Medium
with no microscopic residual tumor:	Low
	None
	None
Expected poster cretive markidity	Mild
Expected postoperative morbidity.	Moderate
	Severe
	Low
mplexity of surgical procedure:	Medium
	High
	Low
Operative rick due to other medical conditions:	Medium
Operative fisk due to other medical conditions.	High
	Pre-Operative Assessment Not Done

Table 16.1: Sample Surgical Assessment Questionnaire

16.5. Long Term Follow-up Questionnaire

Table 16.2: Sample Long Term Follow-up Questionnaire

Question	Response
Did TGCT worsen or recur after study treatment discontinuation?	 No Yes A) Symptoms worse or recurred: Yes / No / Unknown B) Functional Impairment worse or recurred: Yes / No / Unknown C) Radiographic progression: Yes / No / Unknown Other, describe (lost to follow-up, death, etc):
Was/were MRI performed >3 months after study treatment discontinuation?	 No Unknown Yes: Date of assessment:, Result: CR, PR, SD, PD, NE (repeating to enter each MRI until PD or other TGCT intervention)
Was there surgery for TGCT >3 months after study treatment discontinuation?	 No Yes: Date of first surgery after discontinuation:, Reason for surgery: Resection Other, describe:
Was systemic anti-tumor therapy for TGCT given after study treatment discontinuation?	 No Yes: Date of first treatment:, Agent:
Was radiotherapy for TGCT given after study treatment discontinuation?	 No Yes: Date of radiotherapy:

CR = complete response; PR = partial response; SD = stable disease; PD = progressive disease; NE = not evaluable.

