5.8.2. Withdrawal Procedures

If a subject is withdrawn from the study, the Investigator will complete and report the observations as thoroughly as possible up to the date of withdrawal including the date of last dose and the reason for withdrawal.

If the subject is withdrawn due to an AE, the Investigator will follow the subject until the AE has resolved or stabilized.

All subjects who are withdrawn from the study must complete protocol-specified withdrawal procedures.

When a subject discontinues or is permanently withdrawn from the study, the Investigator will notify DS and ensure that the procedures listed in the "post-treatment visit" column in the Schedule of Assessment (Table 16.3) are performed 28 ± 7 days after the subject's last dose of

study drug and prior to initiating any new TGCT therapy, including surgery, whichever occurs first.

The consequence of a subject's withdrawal of all consent will be that no new information will be collected from that subject and added to the existing data or any database. However, every effort should be made to follow all subjects for safety.

The reason for study withdrawal will be recorded. If a subject discontinues study drug to undergo surgery, information about the type of surgery and its outcome must be collected.

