6.3.16. Post-treatment Visit (last dose + 28 days) \pm 7 days

To be performed at 28 ± 7 days after the last dose of study drug.

Before any invasive procedures, the following parameters are to be recorded:

- PROMIS Physical Function Scale
- EQ-5D-5L
- Vital signs including BP, pulse rate, and temperature
- 12-lead ECG

The following procedures are to be performed within (\pm) 7 days of this visit:

- Assessment of concomitant medications including analgesics
- Surgical Assessment Questionnaire
- Weight
- Physical examination
- MRI of the affected joint (for subjects who withdraw from the study for reasons other than progression; local assessment of progression status will be recorded)
- Photographic documentation of tumor
- Third-party range-of-motion assessment of the affected joint

Other procedures to be performed:

- Clinical laboratory tests: serum chemistry, hematology, coagulation, liver function, hormone testing, serum pregnancy testing (if applicable), and urinalysis
- If surgical resection of the tumor is performed within 28 days after the last dose of study drug, obtain details and outcome of the surgery
- AE assessment
- For subjects terminating the study because of progression, document if they plan to undergo any new TGCT therapy, including surgery, during the 28 days period (± 7 days) after their last dose of study drug

6.3.17. End-of-Study or Early Termination Visit (last dose + 12 weeks) ± 7 days

This visit is scheduled 12 weeks \pm 7 days after the last dose of study drug or before any new TGCT therapy, including surgery, whichever occurs first. It is scheduled for subjects who withdraw from the study for reasons other than progression.

• Concomitant medications

- If surgical resection of the tumor is performed within 12 weeks after the last dose of study drug, obtain details and outcome of the surgery
- MRI of the affected joint (with local assessment of progression status) is to be performed within (±) 7 days of the visit
- Photographic documentation of tumor
- Assess if the subject plans to begin any new TGCT therapy, including surgery
- Clinical laboratory tests: serum pregnancy testing (if applicable)
- AE assessment
- Terminate the subject from the study

6.3.18. Long Term Follow-up (every 6 months after end-of-study or early termination visit) ± 2 weeks

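### TGCT surgery after the last study visit but within 3 months of stopping drug has no scheduled contact that records it

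*Combined protocol and SAP*

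**What the plan says.** Collection of early surgery is ordered. Section 6.3.16 (post-treatment visit) says "If surgical resection of the tumor is performed within 28 days after the last dose of study drug, obtain details and outcome", and Section 6.3.17 (end-of-study or early termination visit) says "If surgical resection of the tumor is performed within 12 weeks after the last dose of study drug, obtain details and outcome of the surgery". The surgical-data footnotes to both parts of Table 16.3 (footnote t, and footnote l in the part after Week 25) repeat the two windows.

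The timing of the visits is set separately. Section 5.8.2 puts the post-treatment procedures at 28 ± 7 days after the last dose and ahead of any new TGCT therapy. Section 6.3.17 puts the end-of-study visit at 12 weeks ± 7 days "after the last dose of study drug or before any new TGCT therapy, including surgery, whichever occurs first". Its last listed action is "Terminate the subject from the study", and on who attends it says: "It is scheduled for subjects who withdraw from the study for reasons other than progression". The Table 16.3 footnotes confirm that subjects who exit with radiologic progression have their last evaluation at 28 ± 7 days.

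After that there is only telephone contact every 6 months (Sections 5.9 and 6.3.18), using the form in Section 16.5. Its surgery row asks: "Was there surgery for TGCT >3 months after study treatment discontinuation".

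Section 5.8.2 adds a duty for one group: "If a subject discontinues study drug to undergo surgery, information about the type of surgery and its outcome must be collected".

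**The concern.** A visit held before an operation cannot record that the operation took place, when, or with what result. If that visit is also the subject's last, the task passes to the first long-term call, and the call's surgery question starts only at 3 months. The collection rule and the contact schedule do not fit together for subjects who stop drug for another reason, such as toxicity or progression, and are operated on soon afterwards.

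What is at stake is long-term subject status, a listed exploratory endpoint (Section 3.1.2.3) with a planned summary (Section 10.5.3). The operations at risk are the earliest ones, so any loss runs in one direction. There is a possible knock-on: the form's MRI row is completed until progression or another TGCT intervention. If the intervention is unknown, later scans could be entered as though none had occurred.

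**Working it through.** The plan gives no figure to reproduce. The check compares collection windows in days and looks for any other route to the data.

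**Inputs**
- 12 weeks = 12 × 7 = 84 days after last dose (Section 6.3.17).
- 3 calendar months = 89 to 92 days, depending on the stop date. Table 16.2 gives no day count.
- Last evaluation after radiologic progression: Day 28 ± 7, so Day 21 to 35 (Table 16.3 footnotes).
- Assumption: discontinuation (Table 16.2) and last dose (Sections 6.3.16 and 6.3.17) are the same day.

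**Interval between the last visit and the start of the long-term surgery question**

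1. *No progression, visit on Day 84.* 89 − 84 = 5 and 92 − 84 = 8. Only a seam of 5 to 8 days, so the two rules were evidently meant to meet.
2. *No progression, visit brought forward to Day v.* The interval is 89 − v to 92 − v days. The documents do not say how early v would be. For illustration, Day 30 gives 59 to 62 days and Day 60 gives 29 to 32. Take a subject who stops for toxicity, has the visit on Day 43 and surgery on Day 45 (assumed): the interval is 46 to 49 days. Day 45 is before Day 84, so the 12-week instruction applies, but the visit that carries it is over. Day 45 is also before Day 89, so the literal answer at the call is no.
3. *Leaving with progression.* From Day 28: 89 − 28 = 61 and 92 − 28 = 64 days. With the visit window: 89 − 35 = 54 and 92 − 21 = 71 days. The 28-day instruction ends at Day 28, and the 12-week instruction belongs to a visit these subjects do not have.

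**Other routes**
- Plans for new therapy are recorded (Sections 6.3.16 and 6.3.17, Table 16.3 footnotes). That gives intention, not occurrence, date or outcome.
- Section 5.8.2 covers only subjects who stop drug in order to be operated on.
- Procedures are not adverse events (Section 9.1), so adverse event recording does not reliably pick up the operation.

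**Rows of Table 16.2 side by side**

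| Row | Time limit in question | Response field |
|---|---|---|
| Surgery | more than 3 months after discontinuation | date of the first surgery since discontinuation, no limit |
| Systemic therapy | none | date of first treatment |
| Radiotherapy | none | date |

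The surgery row contradicts its own response field and differs from the other two treatment rows.

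**The case against.** The best defence is that the collection windows are counted from the last dose, not from the visit. Nothing cancels the instruction when a visit is early, and a careful site would follow up the operation. Subjects who go straight to surgery are largely covered by Section 5.8.2, and a visit is usually brought forward because surgery is already planned, so the plan is on file. Table 16.2 is labelled a sample, and the eCRF, which is not in the documents, may have a field for this.

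Much of this stands. A reader might infer that early surgery is simply not collected. The documents do not support that: collection is ordered out to 28 days and 12 weeks. What remains is that no scheduled contact after the operation is named to carry out the order, and that the one later contact screens the event out.

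Three further inferences also fail:
- *That the MRI row needs the same change because it has the same 3-month limit.* It is completed only until progression or another TGCT intervention, so scans after an early operation are outside its scope.
- *That time to first surgery would be biased late, or a surgery rate understated by some number of percentage points.* Neither analysis is planned, and the documents do not say how many subjects will be off treatment.
- *That the main efficacy results are affected.* The primary endpoint is fixed at Week 25, and duration of response ends at documented progression and is otherwise censored (Section 10.5.2).

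**Conclusion.** The point holds in limited form and is minor. Surgery after the last visit but within 3 months of discontinuation, in a subject who did not stop drug for surgery, is recorded at most as a plan if the documents are followed literally. The interval is about 54 to 71 days for subjects leaving with progression. For others it runs from the brought-forward visit to 3 months, or 5 to 8 days if the visit takes place on Day 84.

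This assumes that the sample form is used as printed, that the eCRF has no separate field, and that discontinuation means last dose. How many operations would be missed cannot be derived from the documents. Only the exploratory long-term status summary is affected.

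**What to change.** In Table 16.2, reword the surgery row to ask about surgery for TGCT at any time since study treatment was stopped. This matches its response field and the systemic-therapy and radiotherapy rows. Leave the MRI row as it is.

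In Sections 6.3.16 and 6.3.17 and the surgical-data footnotes to both parts of Table 16.3, add one sentence: when the visit took place before the surgery, surgery within the 28-day or 12-week window is still recorded, at the latest at the first long-term call.

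The cost is one questionnaire row, the matching eCRF field and short wording changes in an amendment. No visit or call is added, though sites will have to obtain the date and outcome of some operations after the subject has been terminated. Subjects who do not consent to long-term follow-up (Section 5.9) have no such call, so for them the data would depend on the site acting on the 28-day and 12-week instructions without it.

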16.6. Schedule of Assessment

Table 16.3: Schedule of Assessment

Schedule of Assessment (Completion of study at Week 25, day before C7D1)

	Day -42 to -1 ^a	C1D1	C1D8 ± 2d	C1D15 ± 2d	C1D22 ± 2d	C2D1 ± 2d	C2D8 ± 2d	C2D15 ± 2d	C2D22 ± 2d	C3D1 ± 7d	C3D15 ± 7d	C4D1 ± 7d	C5D1 ± 7d	C6D1 ± 7d	$\begin{array}{c} C7D1^{b} \\ \pm 7d \end{array}$	Post T ^c ± 7d	End St/Ear. Term. ± 7d	Long term follow-up ± 14d
Procedure	Screen ^a	Week 1	Week 2	Week 3	Week 4	Week 5	Week 6	Week 7	Week 8	Week 9	Week 11	Week 13	Week 17	Week 21	Week 25	LD+28d	LD+12 Week / < new Tx ^d	Every 6 month after End St/Ear. Term
Informed consent	Х																	
Demographics & medical history	Х																	
Height, weight	Х														x ^e	x ^e		
Vital signs, incl. BP, pulse rate, temperature ^f	х	х		х		Х				Х		Х	х	х	х	х		
Physical examination ^g	Х					Х						Х			х	Х		
ECG ^h	Х	Х		Х											Х	Х		
Chemistry, hematology	Х	Х		xi		Х				Х		Х	Х	Х	Х	Х		
Liver tests ^j	Х	Х	Х	Х	Х	Х	Х	Х	Х	Х	Х	Х	Х	Х	Х	Х		
Urinalysis		Х										Х			Х	Х		
Hepatitis panel	Х																	
Coagulation tests k		Х													Х	Х		
Hormone testing ¹	Х	Х													Х	Х		
PROMIS Physical Function Scale	х	x								Х			Х		x	X		
EQ-5D-5L	Х	X								Х			Х		X	Х		
MRI of the affected joint ^m	Х											Х			Х	Х	Х	
Photographic documentation of tumor	Х											Х			Х	Х	Х	

	Day -42 to -1 ^a	C1D1	C1D8 ± 2d	C1D15 ± 2d	C1D22 ± 2d	C2D1 ± 2d	C2D8 ± 2d	C2D15 ± 2d	C2D22 ± 2d	C3D1 ± 7d	C3D15 ± 7d	C4D1 ± 7d	C5D1 ± 7d	C6D1 ± 7d	$\begin{array}{c} \text{C7D1}^{\text{b}} \\ \pm 7\text{d} \end{array}$	Post T ^C ± 7d	End St/Ear. Term. ± 7d	Long term follow-up ± 14d
Procedure	Screen ^a	Week 1	Week 2	Week 3	Week 4	Week 5	Week 6	Week 7	Week 8	Week 9	Week 11	Week 13	Week 17	Week 21	Week 25	LD+28d	LD+12 Week / < new Tx ^d	Every 6 month after End St/Ear. Term
Range of motion assessment ⁿ	Х											Х			Х	Х		
Serum pregnancy test	X ⁰					Х				Х		Х	Х	Х	X	Х	Х	
PK, PDy blood sampling ^p		Х		Х		Х				Х			Х					
Surgical Assessment Questionnaire	Х														х	Х		
Analgesic use assessment	xq	Х		Х		Х				Х		Х	Х	Х	Х	Х		
Dispense study Tx		Х				Х				Х		Х	Х	Х	Х			
Study drug dosing at site ^r		Х		Х											Х			
Tx compliance assessment				Х		Х				Х		Х	Х	Х	Х			
Concomitant medications	Х	Х	Х	Х	Х	Х	Х	Х	Х	Х	Х	Х	Х	Х	Х	Х	Х	
Adverse events ^S	Х	Х	Х	Х	Х	Х	Х	Х	Х	Х	Х	Х	Х	Х	Х	Х	Х	
Collection of surgical data ^t																Х	Х	
AMA ^u	Х		•	•					Х							•		
Subject status ^V																		Х

AE = adverse event; ALT = alanine aminotransferase; AMA = Anti-mitochondrial antibody; AST = aspartate aminotransferase; BP = blood pressure; C = cycle; D/d = Day; ECG = electrocardiogram; End St./Ear. Term. = End-of-Study/Early Termination; FSH = follicle-stimulating hormone; GGT = gamma-glutamyl transferase; incl. = including; LD = last dose; MRI = magnetic resonance imaging; PDy = pharmacodynamic; PK = pharmacokinetic; PROMIS = Patient-reported Outcomes Measurement Information System; Pt = patient; TGCT = tenosynovial giant cell tumor; Tx = treatment.

a Procedures performed as part of patient care within the 42-day period before the first dose of study drug may be used for screening purposes if they conform to protocol requirements and standards. All screening test results must be reviewed prior to dosing to assess the study candidate's eligibility for inclusion.

b The Cycle 7, Day 1 visit (C7D1) applies to patients who are continuing or not continuing the study.

c Patients who exit the study with radiologic disease progression will undergo their last study evaluation 28 ± 7 days after their last dose of study drug and before any new TGCT therapy, including surgery, whichever occurs first. Any planned new TGCT therapy, including the type of surgical procedure, will be recorded. Patients who withdraw from the study with radiologic progression do not undergo an End of Study/Early Termination MRI.

- d Patients who end their study participation with no radiologic disease progression will undergo post-treatment procedures 28 ± 7 days after their last dose of study drug and a final MRI 12 weeks ± 7 days after their last dose of study drug or before any new TGCT therapy, including surgery, whichever occurs first. The latter MRI need not be performed if new TGCT therapy starts within 4 weeks of the Post-treatment visit. Before or at the End-of-Study/Early Termination visit, plans for any new TGCT therapy will be obtained.
- e Weight only.
- f Vital signs should be performed before any invasive procedures are carried out on the same day.
- g In the event of early withdrawal, a physical examination is performed at the Post-treatment visit.
- A standard 12-lead ECG is performed prior to dosing. Patients should be told not to take their morning dose of study drug at home on days when an ECG is performed; instead, they should bring their study drug bottle to the site and take their morning dose upon site instruction. At the C1D1 and C1D15 visits only, the ECG is performed before and 2 hours after dosing. The ECG before dosing should be performed before any invasive procedures are carried out on the same day. The 2 hour post-dose ECG should begin within ± 10 minutes of the 2 hour post-dose time point.
- i Hematology only.
- j Alkaline phosphatase, ALT, AST, total and direct bilirubin, and GGT should be assessed at Screening, weekly for the first 8 weeks (until C3D1) and every 2 weeks for the next month (C3D15 and C4D1), then every month thereafter.
- k Patients receiving concomitant warfarin should have their anti-coagulation status carefully monitored for any necessary dose adjustments (see Section 5.6).
- 1 Women who are not using hormonal contraception must be tested for levels of FSH, LH, progesterone, and estradiol. Hormone testing will not be required for women who have either had an oophorectomy or are post-menopausal. Men must be tested for levels of LH, FSH, and testosterone. Men whose testosterone level is below baseline at the last study visit must be followed until their level has stabilized or returned to baseline.
- m MRI of the affected joint should be performed within 56 days prior to C1D1. The Investigator may request a centrally read blinded MRI to confirm progression, eg, if a subject's mid-study clinical profile or local radiologic assessment indicates progression.
- n A range of motion assessment in the affected joint will be performed by a qualified assessor.
- Women of childbearing potential must have a serum pregnancy test within 14 days of enrollment (or, where different regulations apply, within 72 hours of enrollment). (Women who have documentation of at least 12 months of spontaneous amenorrhea and have an FSH level > 40 mIU/mL will be considered postmenopausal and need not undergo pregnancy testing).
- p Details on blood sampling are found in Table 8.1 (PK) and Section 8.1 (PDy).
- q A diary of analgesic use must be kept for the 7-day period before the first dose of study drug.
- r The morning dose of study drug should be administered at the site on the days indicated.
- s After the patient provides signed informed consent; AEs are monitored throughout the study via safety assessments, observation, and patient reporting (see Section 9.5).
- t If surgical resection of the tumor is performed within the designated time period (28 days for Post-Tx and 12 weeks for End St/Ear Term) after the last dose of study drug, details of the surgery and its outcome should be obtained.
- u Serum sample should be collected for AMA at screening and once severe hepatotoxicity is observed (Section 5.4).
- v Subject status will be collected by telephone contact every 6 months from each subject who consent.

Schedule of Assessment (Study drug continuation after Week 25)

	$C10+D1 \\ \pm 7d^{a}$	Post Tx ± 7 ^b	End St/Ear. Term. ± 7d	Long term follow-up ± 14d	
Procedure	Week 37+	LD+28d	LD+12 Week / < new Tx ^c	Every 6 month after End St/Ear. Term	
Weight		Х			
Vital signs, incl. BP, pulse rate, temperature ^d	Х	Х			
Physical examination ^e	Х	Х			
ECG ^f		Х			
Chemistry, hematology	Х	Х			
Liver tests ^g	Х	Х			
Urinalysis		X			
Coagulation tests h		Х			
Hormone testing ⁱ		X			
PROMIS Physical Function Scale	Х	Х			
EQ-5D-5L	Х	X			
MRI of the affected joint ^j	Х	X	Х		
Photographic documentation of tumor	Х	X	Х		
Range of motion assessment k	Х	Х			
Serum pregnancy test	Х	Х	Х		
Surgical Assessment Questionnaire		Х			
Analgesic use assessment	Х	Х			
Dispense study Tx	Х				
Tx compliance assessment	Х				
Concomitant medications	Х	Х	Х		
Adverse events	Х	Х	Х		
Collection of surgical data ¹		Х	Х		
AMA ^m	Х				
Subject status ⁿ				Х	

AE = adverse event; ALT = alanine aminotransferase; AMA = Anti-mitochondrial antibody; AST = aspartate aminotransferase; BP = blood pressure; C = cycle; D/d = Day; ECG = electrocardiogram; End St./Ear. Term. = End-of-Study/Early Termination; FSH = follicle-stimulating hormone; incl. = including; LD = last dose; MRI = magnetic resonance imaging; PROMIS = Patient-reported Outcomes Measurement Information System; Pt = patient; TCGT = tenosynovial giant cell tumor; Tx = treatment.

- a The procedures are performed at C10+D1 and every 12 weeks thereafter (eg, C13, C16, C19).
- b Patients who exit the study with radiological disease progression will undergo their last study evaluation 28 ± 7 days after their last dose of study drug and before any new TGCT therapy, including surgery, whichever occurs first. Any planned new TGCT therapy, including the type of surgical procedure, will be recorded. Patients who withdraw from the study with radiological progression do not undergo an End of Study/Early Termination MRI.
- c Patients who end their study participation with no radiological disease progression will undergo post-treatment procedures 28 ± 7 days after their last dose of study drug and a final MRI 12 weeks \pm 7 days after their last dose of study drug or before any new TGCT therapy, including surgery, whichever occurs first. The latter MRI need not be performed if new TGCT therapy starts within 4 weeks of the Post-treatment visit. Before or at the End-of-Study/Early Termination visit, plans for any new TGCT therapy will be obtained.
- d Vital signs should be performed before any invasive procedures are carried out on the same day.
- e In the event of early withdrawal, a physical examination is performed at the Post-treatment visit.
- f A standard 12-lead ECG is performed prior to dosing. Patients should be told not to take their morning dose of study drug at home on days when an ECG is performed; instead, they should bring their study drug bottle to the site and take their morning dose upon site instruction.
- g Alkaline phosphatase, ALT, AST, total and direct bilirubin, and GGT should be assessed on Day 1 of every 3 cycles thereafter.
- h Patients receiving concomitant warfarin should have their anti-coagulation status carefully monitored for any necessary dose adjustments (see Section 5.6).
- i Women who are not using hormonal contraception must be tested for levels of FSH, LH, progesterone, and estradiol. Hormone testing will not be required for women who have either had an oophorectomy or are post-menopausal.
- j The Investigator may request a centrally read blinded MRI to confirm progression, eg, if asubject's mid-study clinical profile or local radiologic assessment indicates progression.
- k A range of motion assessment in the affected joint will be performed by a qualified assessor.
- 1 If surgical resection of the tumor is performed within the designated time period (28 days for Post-Tx and 12 weeks for End St/Ear Term) after the last dose of study drug, details of the surgery and its outcome should be obtained.
- m Serum sample should be collected for AMA once severe hepatotoxicity is observed (Section 5.4).
- n Subject status will be collected by telephone contact every 6 months from each subject who consent.
